## 8.6 Height and Weight

Height and body weight will be collected.

## 8.7 Clinical Laboratory Tests

Clinical laboratory tests to be performed include hematology (including coagulation), serum chemistry, urine or serum pregnancy assessments, and urinalysis. The Central Laboratory will be used for safety analysis of all specimens collected. Details on the collection tubes and containers, shipment of samples and reporting of results by the Central Laboratory are provided to investigators in the Central Laboratory Manual.

Because subject enrollment will not permit using Central Laboratory results to assess a subject's meeting inclusion/exclusion criteria, it is expected that local laboratory testing will be used in circumstances where this testing is needed to assess a subject's WBC count or differential, serum transaminase or bilirubin levels, serum creatinine or pregnancy testing.

The total volume of blood collected from each subject will be approximately 4 – 11 mL per visit, or approximately 44 mL (3 tablespoons) over the course of the study. In addition, a blood culture will be collected at Screening and repeated if positive. The preferred volume for each blood culture bottle is 10 mL. However, since these are analyzed locally, site staff should refer to their individual laboratory or manufacturers' recommendation.

Omadacycline  
PTK0796-AP-17202-Version 1.0; 26Mar2018

Paratek Pharma, LLC.  
IND # 75,928 IND # 73,431

### 8.7.1 Central Laboratory Parameters

Clinical laboratory tests will include the following:

**Table 3. Clinical Laboratory Tests (Central)**

Hematology:	Serum Chemistry:

 
• Hematocrit (Hct)
 
• Hemoglobin (Hgb)
 
• Mean corpuscular hemoglobin (MCH)
 
• Mean corpuscular hemoglobin concentration (MCHC)
 
• Mean corpuscular volume (MCV)
 
• Platelet count
 
• Red blood cell (RBC) count
 
• White blood cell (WBC) count with differential
 
	
 
• Alkaline phosphatase (ALP)
 
• Alanine aminotransferase (ALT)
 
• Aspartate aminotransferase (AST)
 
• Blood urea nitrogen (BUN)
 
• Calcium (Ca)
 
• Carbon dioxide (CO2)
 
• Chloride (Cl)
 
• Creatinine
 
• Creatine phosphokinase (CK)
 
• Gamma-glutamyl transpeptidase (GGT)
 
• Lipase
 
• Magnesium
 
• Phosphorus (P)
 
• Potassium (K)
 
• Sodium (Na)
 
• Total bilirubin
 

Pregnancy (all female subjects): 
 
• Serum <math>\beta</math>-human chorionic gonadotropin (<math>\beta</math>-HCG)
 
	

### 8.7.2 Local Laboratory Parameters

#### 8.7.2.1 Pregnancy Assessments

All subjects will have a local urine or serum pregnancy test at the site at the Screening. Urine pregnancy test kits will be provided by the sponsor through the Central Laboratory. If a positive urine or serum pregnancy test result is obtained at the site during Screening, the subject is not to be randomized. A serum sample for serum  $\beta$ -human chorionic gonadotropin ( $\beta$ -hCG) testing will be collected at the Screening visit and sent to the Central Laboratory for confirmation of the local urine or serum pregnancy test results as well as at EOT. If a positive  $\beta$ -hCG result is reported by the Central Laboratory after a subject is enrolled, test article administration should be discontinued (see [Section 8.17.6](#)).

#### 8.7.2.2 Urine Culture and Dipstick Tests

A clean-catch midstream urine sample should be collected, analyzed by urine dipstick test for leukocyte esterase, and optionally sent to the local laboratory for microscopic examination. If sent for microscopic evaluation, the sample should be analyzed for pyuria (WBC count > 10/ $\mu$ L in unspun urine or  $\geq 10$  per high power field in spun urine). Results will be recorded on the eCRF.

The sample will also be used for quantitative urine culture by appropriate methods using a calibrated loop that would identify bacteria at a lower limit of  $1.0 \times 10^3$  colony forming units

(CFU)/mL. A Baseline culture must grow at least 1 and no more than 2 bacterial isolates at  $\geq 1.0 \times 10^5$  CFU/mL each. If more than two bacterial isolates are identified, the culture will be considered contaminated. In general, at any visit, bacteria identified at  $1.0 \times 10^5$  CFU/mL or greater should be considered a bacterial pathogen (probability of true pathogen is greater than probability of contamination). At any visit after Screening, a pathogen of the same species as the Baseline pathogen with a CFU count of  $\geq 1 \times 10^4$  CFU/mL and should be considered a persisting pathogen and should be sent to the central laboratory. At any visit after Screening, any culture with a CFU count of  $< 10^4$  CFU/mL should be considered a microbiologic cure.

Culture results are to include identification of all pathogens to the level of genus and species. *In vitro* antimicrobial susceptibility testing of the isolates to antimicrobial drugs that may be used to treat AP can be performed locally using a standard method chosen by the laboratory.

All bacterial isolates that grow  $\geq 10^3$  CFU/mL (whether at Baseline or post-Baseline) identified by the local laboratory from urine culture will be submitted to the Central Laboratory for verification of genus and species and for standardized MIC testing performed for omadacycline, levofloxacin and a panel of other antibiotics. In the event that local laboratory genus and species identification are not consistent with Central Laboratory results, a back-up isolate should be sent to the Central Laboratory.

Details concerning cultures and shipment to the Central Laboratory will be provided in a Clinical Microbiology Laboratory Manual.

The investigator may use the culture and susceptibility results from the local microbiology laboratory to help guide therapy; however, decisions to continue or discontinue test article should be based on clinical response rather than susceptibility results (as omadacycline susceptibility testing is not available at the local site). The decision to continue or discontinue study treatment should be based on the subject's clinical course and the investigator's clinical judgment. The rationale for this decision should be recorded in source documents.

### 8.7.2.3 Blood Cultures

Two sets of blood cultures (1 set = 1 aerobic bottle + 1 anaerobic bottle) should be collected within the 24 hours prior to the first dose of test article. Each set of blood cultures should be collected by direct venipuncture from independent body sites at least 15 minutes apart. If bacteria are isolated from baseline blood cultures, repeat blood cultures should be collected on the day that the positive blood culture is detected. If subsequent blood cultures are also positive, repeat the blood cultures as necessary until negative blood cultures are obtained. Blood culture isolates should be sent to the Central Laboratory.

## **8.8 Efficacy Assessments**

### **8.8.1 Investigator's Assessment of Clinical Response**

#### **8.8.1.1 Investigator's Assessment of Clinical Response at EOT**

The investigator will determine whether or not the subject meets the criteria of 1 of the following clinical outcomes:

- **Clinical Success:** The complete resolution or significant improvement of the baseline signs and symptoms of AP at the EOT visit such that no additional antimicrobial therapy is required for the current infection.
- **Clinical Failure:** No apparent response to therapy or persistence of signs and symptoms of infection at the EOT visit such that use of alternative or additional systemic antimicrobial therapy for the current infection is required or death prior to the EOT visit.
- **Indeterminate:** EOT visit not completed.

#### **8.8.1.2 Investigator's Assessment of Clinical Response at PTE**

For subjects who were determined to be a clinical success or indeterminate at the EOT visit, the investigator will determine whether or not the subject meets the criteria of 1 of the following clinical outcomes:

- **Clinical Success:** The complete resolution or significant improvement of the baseline signs and symptoms of AP symptoms at the PTE such that no additional antimicrobial therapy is required for the current infection.
- **Clinical Failure:** No apparent response to therapy or persistence of signs and symptoms of infection or reappearance of signs and symptoms at or before the PTE visit such that use of additional systemic antimicrobial therapy for the current infection is required or death at or before the PTE visit.
- **Indeterminate:** PTE visit not completed.

#### **8.8.1.3 Investigator's Assessment of Clinical Response at Final Follow-up**

For subjects that were determined to be a clinical success at the PTE visit, the investigator will determine whether or not the subject meets the criteria of 1 of the following clinical outcomes:

- **Clinical Cure:** The complete resolution or significant improvement of the baseline signs and symptoms of AP at FFU visit such that no additional antimicrobial therapy is required for the current infection.
- **Relapse:** The reappearance of signs and symptoms at or before the FFU Visit such that use of alternative or additional systemic antimicrobial therapy for the current infection.
- **Clinical Failure:** Death between the PTE and Final Follow-up.
- **Indeterminate:** Final Follow-up visit not completed.

Omadacycline  
PTK0796-AP-17202-Version 1.0; 26Mar2018

Paratek Pharma, LLC.  
IND # 75,928 IND # 73,431

## 8.9 Microbiologic Response

Microbiologic outcome at EOT and PTE will be programmatically determined for each pathogen isolated at baseline. Per-pathogen microbiologic response categories are eradication, persistence and indeterminate.

Category	Criteria
Eradication	The demonstration that the baseline bacterial pathogen is reduced to $< 10^4$ CFU/mL on urine culture and negative on repeat blood culture (if positive at baseline)
Persistence	The urine culture taken at the study visit grows $\geq 10^4$ CFU/mL of the baseline pathogen identified at study entry and/or a positive blood culture at the study visit demonstrates the same baseline pathogen. Pathogens that are a persistence at EOT will be considered a persistence at PTE.
Indeterminate	No follow-up urine culture is available, or the follow-up urine culture cannot be interpreted for any reason. For a baseline blood pathogen, no follow-up blood culture is available.

CFU = colony forming units, EOT = end of treatment, PTE = post therapy evaluation.

An overall per-subject microbiologic response at EOT and PTE will be programmatically determined for each subject based on the individual outcomes for each baseline pathogen. For a subject to have a microbiologic response of success, the outcome for each baseline pathogen must be eradicated. If the outcome for any pathogen is persistence, the subject will be considered to have a microbiologic response of failure. Subjects with a persistence at EOT will be considered a persistence at PTE.

Category	Criteria
Success	The outcome of all baseline pathogens must be eradication at the specified visit (EOT or PTE)
Failure	The outcome of at least 1 baseline pathogen is persistence. Subjects with a persistence at EOT will be considered a persistence at PTE.
Indeterminate	The outcome of at least 1 baseline pathogen is indeterminate and there is no outcome of persistence for any baseline pathogen

EOT = end of treatment, PTE = post therapy evaluation.

## 8.10 Modified Patient Symptom Assessment Questionnaire

The subject will report the severity of their pyelonephritis symptoms and how bothersome they are with the Modified Patient Symptom Assessment Questionnaire (mPSAQ). The questionnaire will be completed during each study visit. The subject will rate the severity and how bothersome each symptom on a 4-point scale (no symptom, mild, moderate, severe and not at all, a little, moderately, a lot) and the results will be recorded in the eCRF. The investigator must review the subject's responses and record any AEs as appropriate. See [Appendix 3](#) for the mPSAQ.

## 8.11 Pharmacokinetic Assessments

Instructions will be provided to sites with detailed information on sample collection, handling, and shipment requirements. All samples will be given a unique identifier. The exact clock time of dosing, date and time of last food intake, as well as actual sample collection date and time will be entered on the eCRF.

### 8.11.1 PK Blood Collection and Processing

Blood samples will be collected and analyzed for omadacycline concentration at the following times:

- Just prior to the dose on Day 3 and just prior to last dose of test article;
- 2 to 3 hours after dose on Day 3 and 2 to 3 hours after last dose of test article.

### 8.11.2 PK Urine Collection and Processing

Urine will be collected, the volume recorded, and analyzed for omadacycline concentration at the following times:

- Day 3 to 4: pooled total urine from 0 to 24 hours after the Day 3 dose;
- Day 6 to 7: pooled total urine from 0 to 24 hours after the Day 6 dose

Omadacycline urine concentration data will be used to determine the 24-hr average urinary concentration and amount of drug excreted in the urine in a dosing interval at steady-state.

### 8.11.3 Storing and Shipping of PK Samples

After all PK samples from a single subject have been collected and frozen at - 20°C or colder, the primary samples from each time point can be batched together and carefully packaged and shipped frozen at - 20°C or colder to the central laboratory designated by the sponsor. Samples are to be shipped with sufficient dry ice to remain frozen during overnight transit. For each subject and time point, the remaining stored aliquots will be retained on site at - 20°C or colder until released or requested by the sponsor.

## 8.12 Adverse Events

An AE is any untoward, undesired, or unplanned event in the form of signs, symptoms, disease, or laboratory or physiologic observations occurring in a person given a test article or in a clinical study. The event does not need to be causally related to the test article or clinical study. An AE includes, but is not limited to, the following:

- Any clinically significant worsening of a preexisting condition.
- An AE occurring from overdose of a test article, whether accidental or intentional. Overdose is a dose greater than that specified in the protocol.
- An AE occurring from abuse (eg, use for nonclinical reasons) of a test article
- An AE that has been associated with the discontinuation of the use of a test article

### 8.13 Serious Adverse Events

A serious adverse event (SAE) is an AE that:

- Results in death
- Is life-threatening (see below)
- Requires hospitalization or prolongation of an existing hospitalization (see below)
- Results in a persistent or significant disability or incapacity (see below)
- Results in a congenital anomaly or birth defect
- Additionally, important medical events that may not result in death, be life-threatening, or require hospitalization may be considered SAEs when, based on appropriate medical judgment, they may jeopardize the subject and may require medical or surgical intervention to prevent any one (1) of the outcomes listed above in this definition. Examples of such events include allergic bronchospasm requiring intensive treatment in an emergency room or at home, blood dyscrasias or convulsions that do not result in hospitalization, or development of drug dependency or drug abuse.

Life-threatening refers to immediate risk of death as the event occurred per the reporter. A life-threatening experience does not include an experience, had it occurred in a more severe form, might have caused death, but as it actually occurred, did not create an immediate risk of death. For example, hepatitis that resolved without evidence of hepatic failure would not be considered life-threatening, even though hepatitis of a more severe nature can be fatal. Similarly, an allergic reaction resulting in angioedema of the face would not be life-threatening, even though angioedema of the larynx, allergic bronchospasm, or anaphylaxis can be fatal.

Hospitalization is official admission to a hospital. Hospitalization or prolongation of a hospitalization constitutes criteria for an AE to be serious; however, it is not in itself considered an SAE. In absence of an AE, a hospitalization or prolongation of a hospitalization should not be reported as an SAE by the participating investigator. This is the case in the following situations:

- The hospitalization or prolongation of hospitalization is needed for a procedure required by the protocol
- The hospitalization or prolongation of hospitalization is part of a routine procedure followed by the center (eg, stent removal after surgery). This should be recorded in the study file.
- A hospitalization for a preexisting condition that has not worsened

Disability is defined as a substantial disruption in a person's ability to conduct normal life functions.

If there is any doubt about whether the information constitutes an SAE, the information is treated as an SAE.

## 8.14 Other Reportable Information

Certain information, although not considered an SAE, must be recorded, reported, and followed up as indicated for an SAE. This includes:

- Pregnancy exposure to a test article: If a pregnancy is confirmed, use of the test article must be discontinued immediately. Information about pregnancy exposure includes the entire course of pregnancy and delivery, and perinatal and neonatal outcomes, even if there are no abnormal findings. Both maternal and paternal exposures are considered other reportable information. For exposure involving the female partner of a male subject, the necessary information must be collected from the subject, while respecting the confidentiality of the partner.
- Lactation exposure to a test article with or without an AE
- Overdose of a test article as specified in this protocol with or without an AE
- Inadvertent or accidental exposure to a test article with or without an AE

## 8.15 Overdose

Any administration of omadacycline of greater than 1350 mg within a 24-hour period will be an overdose, regardless of whether the overdose is intentional or accidental, it is a reportable event and the sponsor must be notified within 1 business day. Any administration of greater than 750 mg of levofloxacin in a single administration will be an overdose. In the event that a study subject takes an overdose of test article, the investigator may obtain the subject's treatment assignment by contacting the IxRS. Interactive Response System will also provide a confirmation report of the drug assignment to site personnel. The site personnel will retain this confirmation report. In the case of a potential overdose, the subject should maintain a high level of fluid intake to promote urinary excretion (as recommended in the levofloxacin USPI).

The physician managing the overdose may order any test he/she thinks is necessary to manage the subject properly.

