**Table 1. Description of Treatment Groups**

Group	Test Article	Study Day 1	Study Days 2 to 7	Study Days 8 to 10 a
1	omadacycline	200 mg iv	200 mg iv	200 mg iv
2	omadacycline	200 mg iv	100 mg iv	100 mg iv
3	omadacycline	200 mg iv	300 mg po or 100 mg iv	300 mg po or 100 mg iv
4	omadacycline	200 mg iv	450 mg po or 100 mg iv	450 mg po or 100 mg iv
5	levofloxacin	750 mg iv	750 mg po or 750 mg iv	750 mg po or 750 mg iv

Dosing in all treatment groups is once-per-day.

All iv doses will be administered as continuous infusions over 90 minutes.

All oral doses will be taken in a fasted state (no food, antacids or multivitamins containing multivalent cations [eg, aluminum, magnesium, calcium, bismuth, iron, or zinc] or drink except water for at least 6 hours prior to dosing; after dosing, no food for 2 hours, no dairy products, antacids or multivitamins containing multivalent cations for 4 hours).

iv = intravenous, po = per oral.

a The total duration of treatment for subjects is 7-10 days, up to 14 days of treatment for subjects with bacteremia.

It is possible that not all treatment arms will be enrolling subjects at the same time. Arms may be dropped based on the Bayesian analysis or initiated based on the Bayesian analysis of the ongoing treatment arms. There will always be at least one omadacycline arm and the levofloxacin arm open.

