**Table 2. Dosing Blinded iv and Oral Double-Blind, Double-Dummy Design**

Dosing		Group 1 omadacycline	Group 2 omadacycline	Group 3 omadacycline	Group 4 omadacycline	Group 5 Levofloxacin
Day 1		omadacycline 200 mg iv in 150 mL NS	omadacycline 200 mg iv in 150 mL NS	omadacycline 200 mg iv in 150 mL NS	omadacycline 200 mg iv in 150 mL NS	levofloxacin 750 mg iv in 150 mL saline
Days 2 to 7-10 a, b, c	continue iv	omadacycline 200 mg iv in 150 mL NS	omadacycline 100 mg iv in 150 mL NS	omadacycline 100 mg iv in 150 mL NS	omadacycline 100 mg iv in 150 mL NS	levofloxacin 750 mg iv in 150 mL saline
	switch to po b	omadacycline 200 mg iv in 150 mL NS and three placebo tablets resembling omadacycline and three over- encapsulated placebo tablets resembling levofloxacin	omadacycline 100 mg iv in 150 mL NS and three placebo tablets resembling omadacycline and three over- encapsulated placebo tablets resembling levofloxacin	150 mL NS and two 150 mg omadacycline tablets, one placebo tablet resembling omadacycline, and three over- encapsulated placebo tablets resembling levofloxacin	150 mL NS and three 150 mg omadacycline tablets and three over- encapsulated placebo tablets resembling levofloxacin	150 mL NS and three placebo tablets resembling omadacycline and three over- encapsulated 250 mg levofloxacin tablets

Dosing in all treatment groups is once-per-day.

All iv doses will be administered as continuous infusions over 90 minutes.

All oral doses will be taken in a fasted state (no food, antacids or multivitamins containing multivalent cations [eg, aluminum, magnesium, calcium, bismuth, iron, or zinc] or drink except water for at least 6 hours prior to dosing; after dosing, no food for 2 hours, no dairy products, antacids or multivitamins containing multivalent cations for 4 hours).

iv = intravenous, NS = normal saline, po = per oral.

a The total duration of treatment is 7-10 days, Subjects with bacteremia can continue treatment for up to 14 days.

b Starting on Day 2, per investigator's discretion, subjects may be switched to oral dosing per oral switch criteria.

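### Does it matter that Protocol Sections 8.12 and 8.15 describe overdose differently and Section 8.14 cites neither?

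*Protocol*

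**What the plan says.** Three consecutive parts of the protocol's safety chapter mention overdose.

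- **Section 8.12 (Adverse Events)** lists what counts as an adverse event. One bullet covers events arising from overdose and adds: "Overdose is a dose greater than that specified in the protocol".
- **Section 8.14 (Other Reportable Information)** lists items that are not SAEs but "must be recorded, reported, and followed up as indicated for an SAE". One item is "Overdose of a test article as specified in this protocol with or without an AE". No section number is given.
- **Section 8.15 (Overdose)** gives amounts: "Any administration of omadacycline of greater than 1350 mg within a 24-hour period will be an overdose", and "Any administration of greater than 750 mg of levofloxacin in a single administration will be an overdose". It also sets a one-business-day notice to the sponsor, lets the investigator obtain the assignment from the IxRS when an overdose occurs, and gives one fluid-intake instruction for a potential overdose in any arm.

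Table 1 schedules omadacycline once daily at 100 or 200 mg iv, or 300 or 450 mg po (Group 4 after Day 1: "450 mg po or 100 mg iv"). Levofloxacin is 750 mg by either route. In Table 2 every oral dose is three omadacycline-type tablets and three levofloxacin-type capsules. The active omadacycline content is "two 150 mg omadacycline tablets, one placebo tablet resembling omadacycline" in Group 3 and "three 150 mg omadacycline tablets" in Group 4. Section 7.9 says that oral supplies are blinded.

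**The concern.** Taken literally, 8.12 makes any amount above the scheduled dose an overdose, whereas 8.15 requires a fixed amount to be passed. Section 8.14 carries the reporting duty but names neither. One event could then be reportable on the SAE timetable under one section and not under the other.

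Blinding appears to make this worse. Every subject's oral set looks the same, so a blinded coordinator who learns that a subject took two sets cannot tell from the tablets whether the 8.15 amount has been passed. The answer depends on the arm.

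At stake would be uneven safety reporting between sites or arms and, at worst, an excess dose that the sponsor hears of late.

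**Working it through.** **Inputs.** Scheduled doses come from Protocol Table 1, tablet contents from Table 2, overdose amounts from Section 8.15, and the iv-to-po interval of 12 to 24 hours from Section 7.6.6. The plan gives no derived figure to reproduce.

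**Step 1: distance between the two wordings.** Ratio = amount in 8.15 / scheduled dose.

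| Scheduled dose | Ratio |
|---|---|
| Omadacycline 450 mg po | 1350/450 = 3.0 |
| Omadacycline 300 mg po | 1350/300 = 4.5 |
| Omadacycline 200 mg iv | 1350/200 = 6.75 |
| Omadacycline 100 mg iv | 1350/100 = 13.5 |
| Levofloxacin 750 mg | 750/750 = 1.0 |

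For a single levofloxacin administration the wordings coincide. For omadacycline they part between the scheduled dose and a 24-hour total of 1350 mg. They also part for a second 750 mg levofloxacin dose given in error on the same day: it exceeds the once-daily schedule, but neither administration is above 750 mg.

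**Step 2: a doubled oral set taken at once.**

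| Group | Active oral drug | Above scheduled dose | Above the 8.15 amount |
|---|---|---|---|
| 1, 2 | 0 mg | no | no |
| 3 | 4 x 150 = 600 mg | yes | no |
| 4 | 6 x 150 = 900 mg | yes | no |
| 5 | 6 x 250 = 1500 mg | yes | yes |

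With a 200 mg iv dose in the same 24 hours, Groups 3 and 4 reach 600 + 200 = 800 mg and 900 + 200 = 1100 mg, still below 1350 mg.

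**Step 3: does correct dosing trip either wording?** A switch at 12 hours gives 200 + 300 = 500 mg or 200 + 450 = 650 mg omadacycline within 24 hours. For levofloxacin it gives 750 + 750 = 1500 mg in two administrations, neither above 750 mg. All of this is scheduled dosing, so neither wording classes it as overdose.

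**Step 4: which text governs?** The 8.12 sentence sits inside a bullet on the scope of adverse events and carries no reporting duty of its own. Section 8.14 points to overdose as the protocol specifies it. The next section is headed Overdose and is the only place with amounts, a notice period and a procedure. A site would naturally turn there. Section 8.15 is also explicit about timing: a 24-hour period for omadacycline and a single administration for levofloxacin.

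**Step 5: what would be lost under the narrower reading?**

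- Any adverse event after an excess dose is recorded under Section 8.17 from consent to Final Follow-up, and any serious one follows 8.17.1, whatever the dose is called.
- A separate item in 8.14 covers inadvertent or accidental exposure and carries the same SAE-type duty.
- Section 8.16 routes medication errors to the sponsor, and Section 7.15 requires dosing discrepancies to be documented.
- The unblinded pharmacist prepares iv doses (Section 7.9), so an error in an iv amount can be recognised without unblinding the investigator.

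**Step 6: what in the SAP depends on it?** The SAP neither defines nor tabulates overdose. Exposure and compliance (SAP Section 8.2) count doses. The clinically evaluable population (SAP Section 4.4) requires at least 80% compliance and sets no upper limit, so that criterion removes nobody for an excess dose.

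**The case for a change.** The strongest case for acting is that 8.12 is an express definition, in the same protocol, and nothing subordinates it to 8.15. The band between the two is wide for omadacycline. The reporting routes differ: SAE-type items go within one business day or 24 hours, while 8.16 sends other medication errors on a separate form with no stated deadline. A deliberate excess is not clearly accidental exposure or human error. Subjects at approved outpatient sites return unused tablets (Appendix 1), so unsupervised oral dosing can happen. The IxRS route in 8.15 opens once an overdose has occurred, which is what a blinded investigator may not yet know.

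Parts of this stand. The wordings do differ, and the reporting route for a symptom-free omadacycline excess of up to 1350 mg, or a repeated levofloxacin dose, depends on which is followed.

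The rest carries less weight. Oral doses are given by study staff at visits (Section 7.6.6), and outpatient administration is an approved exception. The investigator can also unblind in an emergency without prior consultation (Section 7.11). Dependence of the class on the arm follows from having drug-specific amounts in a blinded trial. Asking for a rule that blinded staff can apply would reach into the content of a clinical safety rule, which is beyond a consistency check.

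**Conclusion.** The plan can stand. Sections 8.12 and 8.15 are worded differently, and 8.14 lacks a pointer to the section it relies on, but 8.15 is the evident governing text and sites can be expected to use it. If the protocol is amended for another reason, reconciling the three wordings would be ordinary housekeeping. No view is taken here on which amount or form of definition is right.

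The effect on results is nil: no endpoint, analysis population, sample size, interim criterion or planned safety table uses an overdose classification. The effect on safety reporting is at most the route and timing of notice for an excess dose that causes no SAE, falls under one wording only, and is not already caught as accidental exposure. No such lost event has been shown.

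This rests on three assumptions: sites read 8.14 as pointing to 8.15; staff-given dosing keeps unsupervised excess uncommon; and the 24-hour wording for omadacycline means the total over that period.
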